6.3 Protocol Deviations

Protocol deviations data will be summarized by type of deviations (eg, deviations in entry criteria, dosing, concomitant medication, procedural, etc.). In addition, a patient listing will be provided describing the deviations for each subject.

7 Analysis of Demographic and Baseline Characteristics

Baseline demographic characteristics including age, race, ethnicity, gender, weight, height, and BMI will be summarized by descriptive statistics (frequency, mean, median, standard deviation, maximum, minimum, and percentage when applicable)

8 Efficacy Analysis

Efficacy is secondary objective for the study. Efficacy endpoints are as follows:

- 1) Change from baseline in CGI-S score, by trial week and at the last visit (ie, Week 26/ET or Week 52/ET);
- 2) Mean CGI-I score, by trial week and at the last visit (ie, Week 26/ET or Week 52/ET);
- 3) Change from baseline in SDS score, by trial week and at the last visit (ie, Week 26/ET or Week 52/ET);
- 4) Change from baseline in IDS-SR Total Score, by trial week and at the last visit (ie, Week 26/ET or Week 52/ET).

Descriptive statistics will be provided for each endpoint. The analysis will be carried out on the Efficacy Sample. Descriptive statistics will be summarized at each trial visit using the OC data set and at the last visit using the LOCF data set.

9 Safety Analyses

The primary safety analysis is the frequency and severity of AEs (see Section 9.1). Other standard safety variables to be analyzed include clinical laboratory tests, vital signs, ECGs, body weight, waist circumference, and BMI. In addition, data from the following safety scales will be evaluated: SAS, AIMS, BARS, C-SSRS, and MSFQ. Analyses regarding safety and tolerability will be conducted based on the Safety Sample, which is defined in Section 5.1. In general, baseline measurements of safety variables are defined as their last measurements prior to the first dose of open-label brexpiprazole.

9.1 Adverse Events

All AEs will be coded by Medical Dictionary for Regulatory Activities (MedDRA) system organ class and preferred term. The incidence of the following events will be summarized:

- TEAEs by severity
- Potentially drug-related TEAEs
- TEAEs with an outcome of death
- Serious TEAEs
- Discontinuations due to TEAEs

A TEAE is defined as an AE that starts after the first dose of IMP or an AE that is reported at baseline and increases in intensity or becomes serious or trial drug-related or results in death, discontinuation, interruption or reduction of IMP.

In addition, incidence of TEAE during Treatment Phase of at least 5% by SOC and PT will be provided.

Incidence of TEAEs by SOC and PT will be summarized for sex, race and age subgroups.

EPS-related AEs will be grouped into five categories.

- 1) Dystonic Events, which include cervical spasm, dystonia, emprosthotonus, muscle contractions involuntary, muscle rigidity, muscle spasms, muscle spasticity, myotonia, nuchal rigidity, oculogyration, opisthotonus, pleurothotonus, risus sardonicus, torticollis, and trismus;
- 2) Parkinsonian Events, which include akinesia, asterixis, athetosis, bradykinesia, cogwheel rigidity, essential tremor, extrapyramidal disorder, freezing phenomenon, gait festinating, hypertonia, hypokinesia, hypokinesia neonatal, intention tremor, masked facies, parkinson's disease, parkinsonian crisis, parkinsonian gait, parkinsonian rest tremor, parkinsonism, tremor, and tremor neonatal;
- 3) Akathisia Events, which include akathisia, hyperkinesia, and psychomotor hyperactivity;
- 4) Dyskinetic Events, which include ballismus, buccoglossal syndrome, choreoathetosis, clumsiness, dyskinesia, dyskinesia neonatal, dyskinesia oesophageal, fumbling, nodding of head, on and off phenomenon, and tardive dyskinesia;
- 5) Residual Events, which include chorea, huntington's chorea, muscle twitching, and myoclonus.

Incidence of EPS-related TEAEs will be summarized by EPS category. This summary will also be provided by ADT.

9.2 Clinical Laboratory Data

Summary statistics for changes from baseline in the routine clinical laboratory measurements, prolactin concentrations, coagulation parameters (PT, aPTT, and INR), HbA1c, cortisol, ACTH, and TSH will be provided. In addition, potentially clinically significant results in laboratory tests identified using prospectively defined criteria will be summarized.

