^bIf a subject discontinues prematurely before Week 26, procedures noted for Week 26 must be completed at the early termination (ET) visit. Subjects who have completed 26 weeks or more, will have the Week 26/ET procedures at their next scheduled visit.

^cConsists of telephone contact or clinic visit (investigator's discretion) for evaluation of safety and applies to all subjects (completers and early withdrawals).

^dInformed consent for Trial 331-10-238 will occur at Screening/Baseline and must be obtained before any trial-related procedures specific to the open-label trial are performed.

^eUpdate, if necessary.

^fImprovement should be based on the subject's status at the last scheduled visit of the prior double-blind phase 3 trial.

^gVital signs include body weight, body temperature, systolic blood pressure (SBP), diastolic blood pressure (DBP), and heart rate. Blood pressure and heart rate will be measured in the following order: supine, sitting, and standing after the subject has been in each position for at least 3 minutes. Vital signs scheduled for the same visit as blood samples are to be completed before blood is drawn.

^hStandard 12-lead ECGs will be performed after the subject has been supine and at rest for \geq 5 minutes prior to the ECG. A central ECG service will be utilized to review all ECGs in order to standardize interpretations for the safety analysis. In addition, ECG results will be evaluated at the investigational site to monitor safety during the trial. Subjects will be enrolled in Trial 331-10-238 based on the screening/baseline ECG results from the trial site. If the screening/baseline ECG results from the central reader (ie, the last scheduled visit of the prior double-blind phase 3 trial), when available, indicate a QTcF

≥ 450 msec at screening/baseline, the investigator must contact the medical monitor to discuss the subject's continued participation in the trial. ECGs scheduled for the same visit as blood samples are to be completed before blood is drawn.

ⁱIncludes hematology (including PT, aPTT, and INR), serum chemistry (including prolactin and TSH, with reflex to free thyroxine [T₄] if the result for TSH is abnormal), and urinalysis.

^jSubjects must be fasting for a minimum of 8 hours prior to blood draws for screening/baseline laboratory assessments (ie, the last scheduled visit of the prior double-blind phase 3 trial).

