A central laboratory designated by the sponsor will be used for all laboratory testing required during the trial. The central laboratory should be used for all laboratory testing whenever possible (including unscheduled and follow-up labs, if needed). In cases where an immediate result is required for a particular laboratory test, the sample should be divided and sent to both a local laboratory and the designated central laboratory. Urine will be collected and blood will be drawn from subjects at the scheduled visits designated in Table 3.6-1. Additional urine and blood samples may be collected for further evaluation of safety as warranted by the investigator's judgment. Screening/baseline laboratory assessments will be performed after a minimum 8-hour fast per the protocol instructions for the double-blind phase 3 trials. All subjects must be fasting for a minimum of 8 hours prior to the blood draw at Week 26/ET and should be fasting for a minimum of 8 hours prior to all other blood draws during the Treatment Phase, if possible. If a subject is not fasting at a visit other than Week 26/ ET, the blood draw should still be performed and the status documented as nonfasting on the laboratory requisition sheet. The Week 26/ET blood draw must be rescheduled to accommodate the fasting requirement. Reports from the central laboratory should be filed with the source documents for each subject. The central laboratory will provide laboratory results to the sponsor electronically.

Table 3.6.2.1-1 Safety Clinical Laboratory Tests

Hematology:	Serum Chemistry:
WBC count with differential	ALP
RBC count	ALT or SGPT
Hematocrit	AST or SGOT
Hemoglobin	BUN
Platelet count	CPK
	Creatinine
Urinalysis:	LDH
pH	Total bilirubin
Specific gravity	Triglycerides
Protein	Cholesterol (total, LDL, and HDL)
Ketones	Calcium
Glucose	Chloride
Blood	Glucose
Microscopic exam (performed only if any part of the urinalysis is not negative)	Insulin
	Magnesium
	Bicarbonate
Urine Drug Screens:	Inorganic phosphorous
Amphetamines	Sodium
Barbiturates	Potassium
Benzodiazepines	Total protein
Cannabinoids	Uric acid
Cocaine	GGT
Marijuana	Prolactin
Methadone	Albumin
Opiates	
Phencyclidine	Additional Tests:
Propoxyphene	Urine pregnancy (WOCBP) ^a
	TSH, with reflex to free T ₄ if TSH is abnormal
Other:	PT, aPTT, and INR
Blood alcohol	HbA1c

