screening/baseline ECG results from the central reader (ie, ~~Week 14 visit of Trial 331-10-227 or Trial 331-10-228~~*the last scheduled visit of the prior double-blind phase 3 trial*), when available, indicate a QTcF \geq 450 msec at screening/baseline, the investigator must contact the medical monitor to discuss the subject's continued participation in the trial. ECGs scheduled for the same visit as blood samples are to be completed before blood is drawn.

j Includes hematology (including PT, aPTT, and INR), serum chemistry (including prolactin and TSH, with reflex to free thyroxine [T₄] if the result for TSH is abnormal), and urinalysis.

k Subjects must be fasting for a minimum of 8 hours prior to blood draws for screening/baseline laboratory assessments (ie, ~~Week 14 visit of Trial 331-10-227 and Trial 331-10-228~~*the last scheduled visit of the prior double-blind phase 3 trial*).

l Clinical laboratory tests should be drawn fasting, if possible, but must be drawn after a minimum 8-hour fast at Week 52/ET. Vital sign and ECG assessments should be completed before any blood samples are collected.

m ~~A fasting blood sample for analysis of ACTH, cortisol, and HbA1c must be drawn at Screening/Baseline from subjects entering Trial 331-10-238 after completing Phase A+ of Trial 331-10-227 or Trial 331-10-228. This is not required for subjects entering Trial 331-10-238 from Phase B of Trial 331-10-227 or Trial 331-10-228 because the screening/baseline values will be obtained from the last visit of the double-blind protocols.~~

n A urine drug screen and a blood alcohol test are required at the designated times, but either or both can be conducted at any time during the trial at the discretion of the investigator.

o All positive urine pregnancy test results must be confirmed by a serum test. Subjects with a positive serum pregnancy test result at Screening/Baseline must not be enrolled in Trial 331-10-238 and subjects with a positive serum pregnancy test result during the trial must discontinue treatment and be withdrawn from the trial. Pregnancy tests can be performed at any point during the trial if pregnancy is suspected.

p "Since Last Visit" C-SSRS form.

q AE recording will begin with the signing of the ICF for Trial 331-10-238.

r All prescription and non-prescription medications taken during the trial will be recorded as concomitant medications. Details of prohibited and restricted medications are provided in [Section 4](#).

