^hStandard 12-lead ECGs will be performed after the subject has been supine and at rest for ≥ 5 minutes prior to the ECG. A central ECG service will be utilized to review all ECGs in order to standardize interpretations for the safety analysis. In addition, ECG results will be evaluated at the investigational site to monitor safety during the trial. Subjects will be enrolled in Trial 331-10-238 based on the screening/baseline ECG results from the trial site. If the screening/baseline ECG results from the central reader (ie, the last scheduled visit of the prior double-blind phase 3 trial), when available, indicate a QTcF ≥ 450 msec at screening/baseline, the investigator must contact the medical monitor to discuss the subject's continued participation in the trial. ECGs scheduled for the same visit as blood samples are to be completed before blood is drawn.

ⁱIncludes hematology (including PT, aPTT, and INR), serum chemistry (including prolactin and TSH, with reflex to free thyroxine [T4] if the result for TSH is abnormal), and urinalysis.

^j Subjects must be fasting for a minimum of 8 hours prior to blood draws for screening/baseline laboratory assessments (ie, the last scheduled visit of the prior double-blind phase 3 trial).

^k Clinical laboratory tests should be drawn fasting, if possible, but must be drawn after a minimum 8-hour fast at Week 26/ET. Vital sign and ECG assessments should be completed before any blood samples are collected.

^l A urine drug screen and a blood alcohol test are required at the designated times, but either or both can be conducted at any time during the trial at the discretion of the investigator.

^m All positive urine pregnancy test results must be confirmed by a serum test. Subjects with a positive serum pregnancy test result at Screening/Baseline must not be enrolled in Trial 331-10-238 and subjects with a positive serum pregnancy test result during the trial must discontinue treatment and be withdrawn from the trial. Pregnancy tests can be performed at any point during the trial if pregnancy is suspected.

ⁿ “Since Last Visit” C-SSRS form.

^o AE recording will begin with the signing of the ICF for Trial 331-10-238.

^p All prescription and non-prescription medications taken during the trial will be recorded as concomitant medications. Details of prohibited and restricted medications are provided in [Section 4](#).

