Appendix 2 **Criteria for Identifying Laboratory Values of Potential Clinical Relevance**

Laboratory Tests	Criteria
Chemistry	
AST (SGOT)	$\geq 3 \times$ upper limit of normal (ULN)
ALT (SGPT)	$\geq 3 \times$ ULN
Alkaline phosphatase	$\geq 3 \times$ ULN
LDH	$\geq 3 \times$ ULN
BUN	≥ 30 mg/dL
Creatinine	≥ 2.0 mg/dL
Uric Acid	
Men	≥ 10.5 mg/dL
Women	≥ 8.5 mg/dL
Bilirubin (total)	≥ 2.0 mg/dL
CPK	$\geq 3 \times$ ULN
Prolactin	$>$ ULN
Hematology	
Hematocrit	
Men	$\leq 37\%$ and decrease of ≥ 3 percentage points from Baseline
Women	$\leq 32\%$ and decrease of ≥ 3 percentage points from Baseline
Hemoglobin	
Men	≤ 11.5 g/dL
Women	≤ 9.5 g/dL
White blood count	$\leq 2,800/\text{mm}^3$ or $\geq 16,000/\text{mm}^3$
Eosinophils	$\geq 10\%$
Neutrophils	$\leq 15\%$
Absolute neutrophil count	$\leq 1,000/\text{mm}^3$
Platelet count	$\leq 75,000/\text{mm}^3$ or $\geq 700,000/\text{mm}^3$
Urinalysis	
Protein	Increase of ≥ 2 units
Glucose	Increase of ≥ 2 units
Casts	Increase of ≥ 2 units
Additional Criteria	
Chloride	≤ 90 mEq/L or ≥ 118 mEq/L
Potassium	≤ 2.5 mEq/L or ≥ 6.5 mEq/L
Sodium	≤ 126 mEq/L or ≥ 156 mEq/L
Calcium	≤ 8.2 mg/dL or ≥ 12 mg/dL
Glucose	
Fasting	≥ 100 mg/dL
Non-Fasting	≥ 200 mg/dL
Total Cholesterol, Fasting	≥ 240 mg/dL
LDL Cholesterol, Fasting	≥ 160 mg/dL
HDL Cholesterol, Fasting	
Men	< 40 mg/dL
Women	< 50 mg/dL
Triglycerides, Fasting	≥ 150 mg/dL

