- CT-8.6.3.2 Incidence of Treatment-emergent Adverse Events Resulting in Discontinuation from Study Medication by System Organ Class, MedDRA Preferred Term and Severity – 52-Week Enrollers
- CT-8.6.3.3 Incidence of Treatment-emergent Adverse Events Resulting in Discontinuation from Study Medication by System Organ Class, MedDRA Preferred Term and Severity – 26-Week Enrollers
- CT-8.7.1 Incidence of TEAE Occurring in at Least 5 Percent of Patients by System Organ Class and MedDRA Preferred Term in the Total Group – All Subjects
- CT-8.7.2 Incidence of TEAE Occurring in at Least 5 Percent of Patients by System Organ Class and MedDRA Preferred Term in the Total Group – 52-Week Enrollers
- CT-8.7.3 Incidence of TEAE Occurring in at Least 5 Percent of Patients by System Organ Class and MedDRA Preferred Term in the Total Group – 26-Week Enrollers
- CT-8.8.1.1 Incidence of TE EPS-related AEs by EPS Category and MedDRA Preferred Term – All Subjects
- CT-8.8.1.2 Incidence of TE EPS-related AEs by EPS Category and MedDRA Preferred Term – 52-Week Enrollers
- CT-8.8.1.3 Incidence of TE EPS-related AEs by EPS Category and MedDRA Preferred Term – 26-Week Enrollers
- CT-8.8.2.1 Incidence of TE EPS-related AEs by EPS Category and MedDRA Preferred Term by ADT – All Subjects
- CT-8.8.2.2 Incidence of TE EPS-related AEs by EPS Category and MedDRA Preferred Term by ADT – 52-Week Enrollers
- CT-8.8.2.3 Incidence of TE EPS-related AEs by EPS Category and MedDRA Preferred Term by ADT – 26-Week Enrollers

CT-9.1 Listing of Deaths

CT-9.2.1 Listing of Serious Adverse Events – All Subjects

CT-9.2.2 Listing of Serious Adverse Events – 52-Week Enrollers

CT-9.2.3 Listing of Serious Adverse Events – 26-Week Enrollers

CT-9.3.1 Listing of Discontinuations from Study Medication Due to Adverse Events – All Subjects

CT-9.3.2 Listing of Discontinuations from Study Medication Due to Adverse Events – 52-Week Enrollers

CT-9.3.3 Listing of Discontinuations from Study Medication Due to Adverse Events – 26-Week Enrollers

CT-10.1.1.1 Mean Change from Baseline in Clinical Laboratory Test Results - Serum Chemistry – All Subjects

CT-10.1.1.2 Mean Change from Baseline in Clinical Laboratory Test Results - Serum Chemistry – 52-Week Enrollers

CT-10.1.1.3 Mean Change from Baseline in Clinical Laboratory Test Results - Serum Chemistry – 26-Week Enrollers

CT-10.1.2.1 Mean Change from Baseline in Clinical Laboratory Test Results - Hematology – All Subjects

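### Change-from-baseline summaries for glucose, insulin, triglycerides and cholesterol carry no fasting rule, so interim-visit and carried-forward values can be confounded by meals

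*SAP*

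**What the plan says.** **Analysis.** SAP 9.2 promises "Summary statistics for changes from baseline in the routine clinical laboratory measurements, prolactin concentrations, coagulation parameters" together with HbA1c, cortisol, ACTH and TSH. The planned output is "Mean Change from Baseline in Clinical Laboratory Test Results - Serum Chemistry", produced for all subjects, 52-week enrollers and 26-week enrollers. Neither the text nor the table titles mention fasting status. SAP 5.2 uses observed cases at each visit and LOCF at the last visit.

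**Collection.** Protocol Table 3.6.2.1-1 places glucose, insulin, triglycerides and total, LDL and HDL cholesterol in the serum chemistry panel. At baseline, subjects "must be fasting for a minimum of 8 hours prior to blood draws for screening/baseline laboratory assessments" (Table 3.6-1, footnote j). On treatment, footnote k reads: "Clinical laboratory tests should be drawn fasting, if possible, but must be drawn after a minimum 8-hour fast at Week 26/ET". If a subject has not fasted at another visit, Protocol 3.6.2.1 says that "the blood draw should still be performed and the status documented as nonfasting on the laboratory requisition sheet". A Week 26/ET draw must instead be rescheduled.

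**Where the SAP does use fasting status.** SAP Appendix 2 has two glucose limits, 100 mg/dL fasting and 200 mg/dL non-fasting. Its lipid limits are labelled as fasting, for example "LDL Cholesterol, Fasting".

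**The concern.** The baseline is required to be fasting, and some later samples are allowed not to be. For a subject who has eaten before an interim draw, the change is a fed value minus a fasted value. The requirement is one-sided, so these differences do not average out. The trial is open-label and every subject receives brexpiprazole, so no concurrent control group shares the meal effect and cancels it.

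Appendix 2 shows that the sponsor regards fasting status as material for these analytes, but the distinction is not carried into the change tables. The SAP also lists tables on treatment-emergent changes in lipids and glucose and on metabolic syndrome, so metabolic change is a question the trial intends to address. At stake is whether the interim rows, and part of the last-visit row, can be read as change on treatment.

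**Working it through.** The plan states no figure on this point and has no power calculation, so there is nothing to reproduce. The check sets out the fasting rules, counts the affected visits and shows how the bias would scale.

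**1. Fasting rule by draw**

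| Draw | Rule | Source |
|---|---|---|
| Baseline | Mandatory, at least 8 hours | Protocol 3.6.2.1; Table 3.6-1, footnote j |
| Week 14, current schedule | If possible; otherwise drawn and recorded as nonfasting | Protocol 3.6.2.1; footnote k |
| Week 26/ET, current schedule | Mandatory; rescheduled if not met | Protocol 3.6.2.1 |
| Weeks 1, 4, 8, 14, 26, 38, pre-Amendment 3 | If possible | Earlier schedule reproduced in Protocol Appendix 16 |
| Week 52/ET, pre-Amendment 3 | Mandatory | Same |

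The earlier schedule still matters because SAP 5.1 reports 52-week enrollers as a cohort. A fast was not mandatory at 1 of 2 on-treatment laboratory visits on the current schedule (1/2 = 50%) and at 6 of 7 on the earlier one (6/7 = 86%).

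**2. Bias at an interim visit.** Let q be the share of non-fasting samples and D the mean non-fasting minus fasting difference. With a fasting baseline, the mean change is shifted by q × D. The documents give neither q nor D, so the values below are assumptions.

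| q | D = 20 mg/dL | D = 40 mg/dL |
|---|---|---|
| 0% | 0 | 0 |
| 5% | 0.05 × 20 = 1 | 0.05 × 40 = 2 |
| 10% | 0.10 × 20 = 2 | 0.10 × 40 = 4 |
| 20% | 0.20 × 20 = 4 | 0.20 × 40 = 8 |
| 30% | 0.30 × 20 = 6 | 0.30 × 40 = 12 |

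D will differ by analyte, and insulin has its own units, so the table shows scaling only. For glucose, the two limits in Appendix 2 imply that the sponsor expects higher values when the subject has eaten.

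**3. Bias at the LOCF last visit.** Let f be the share of subjects whose last value is carried from an interim visit because the fasting end-of-treatment draw is missing. The shift is f × q × D. With D = 40 mg/dL, assumed values of f = 5% and q = 5% give 0.05 × 0.05 × 40 = 0.1 mg/dL. With f = 20% and q = 30% the shift is 0.20 × 0.30 × 40 = 2.4 mg/dL.

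**4. The All Subjects row at Week 26.** Protocol 3.6.1.8 moved ongoing subjects who had not reached Week 26 to the Amendment 3 schedule, so their Week 26 draw must be fasting. Only draws taken at Week 26 before Amendment 3 fell under the looser rule. If these make up a share w of the row, the shift is w × q × D; w is not given.

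**5. After the fix.** With fasting pairs only, q = 0, and the meal term is zero at every visit and at the last visit.

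**The case against.** The strongest reply is that the protocol already controls the comparison that matters most. Week 26/ET must be fasting, and withdrawn subjects are to have the same end-of-treatment procedures. Fasting is also the stated procedure at Week 14 (Protocol 3.6.1.6); a non-fasting draw is a fallback, and its frequency could be low or nil. HbA1c change is summarised at the same visits, Appendix 2 applies fasting-specific limits, and the primary outcome is adverse events. Finally, only table titles are public, so the absence of a fasting split is inferred from silence.

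Much of this stands, and it rules out several stronger readings that a reader might infer:

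- That metabolic changes as a whole reflect meals rather than drug. The end-of-treatment comparison is fasting to fasting, and a meal effect adds to any drug effect; it does not replace it.
- That the 52-week and 26-week enroller tables are not comparable at Week 26. The transition rule makes the mixing partial.
- That the trend must show an artificial fall from Week 14 to Week 26. This depends on an unknown non-fasting share, and it does not arise from the rule for subjects who had both draws before Amendment 3.
- That the bias rivals the drug effect. The documents state no expected metabolic effect.

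What remains is the missing rule. HbA1c does not address triglycerides or cholesterol. Appendix 2 governs threshold counts, not means. Protocol 3.6.1.8 asks for end-of-treatment evaluations in early withdrawals only where possible, so an interim value can become the last value. A programmer following SAP 9.2 as written would pool all samples at a visit.

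**Conclusion.** The concern holds for interim visits and for last-visit values carried forward from them. SAP 9.2 and CT-10.1.1.x set samples that may be non-fasting against a baseline that must be fasting, with no rule to separate them. It does not hold for observed Week 26/ET or Week 52/ET values when the protocol is followed. In the All Subjects row at Week 26 it applies only to draws taken before Amendment 3.

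The absence of a stated rule is certain; the size of any bias is not. The illustrative 0 to 12 mg/dL at an interim visit and 0.1 to 2.4 mg/dL at the LOCF last visit rest entirely on assumed values of q, D and f. If all interim draws were fasting, the bias is zero. These are descriptive safety tables and the primary adverse-event analysis is unaffected, but the gap is cheap to close and worth closing.

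**What to change.** In SAP 9.2 and CT-10.1.1.x, state that change from baseline in glucose, insulin, triglycerides and total, LDL and HDL cholesterol is computed only from pairs in which both the baseline and the on-treatment sample are recorded as fasting (at least 8 hours). Apply this at each visit and at the last visit, and allow only fasting values to be carried forward. List or summarise non-fasting values separately.

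Confirm that the status written on the requisition sheet reaches the electronic laboratory data. Appendix 2 cannot be programmed without it, so the variable should already be needed.

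The cost is a short SAP addition and one filter, with fewer subjects in the interim rows. Showing the number of fasting pairs in each row would make that loss visible.
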